## 4.1 Sample size justification

- Part-1 (Single-dose):

A sample size of approximately 16 subjects per cohort (six fosmanogepix low-dose, six fosmanogepix high-dose, four placebo) has been chosen based on the need to minimize first exposure of healthy adult Chinese subjects to study drug, and the requirement to provide adequate PK and safety and tolerability data at each cohort and dose level.

- Part-2 (Multiple-dose):

A sample size of approximately 10 subjects per cohort (eight fosmanogepix, two placebo) has been selected to provide adequate PK and safety and tolerability data for each cohort.

## 4.2 Analysis sets

For purposes of analysis, the following analysis sets are defined.

### 4.2.1 Enrolled set

The enrolled set consists of all randomized subjects. Subjects will be analyzed according to the planned treatment.

### 4.2.2 Safety set

The safety set consists of all randomized subjects who have received at least one dose of study drug. Subjects will be analyzed according to the drug they actually received.

### 4.2.3 Pharmacokinetic set

The PK set consists of all randomized subjects who have received at least one dose of study drug and have at least one post-baseline measurable concentration of manogepix. Subjects will be analyzed according to the drug they actually received.

## 4.3 Other important considerations

### 4.3.1 Definition of baseline

Unless otherwise specified, baseline is defined as the last non-missing assessment prior to the first study drug administration. Both scheduled and unscheduled visits and assessments will be used in determining baseline.

### 4.3.2 Study day calculation and visit windows

Visit windowing approaches will not be used for this study, and visit based summaries will include scheduled assessments only.

The following conventions will be used to calculate analysis study day:

- Day 1 is the day of first study drug administration. Day -1 is the day before Day 1. No Day 0 is defined for this study.

- Prior to Day 1, the algorithm is:  
Study Day = visit/examination date – date of first study drug administration
- For Day 1 and subsequent days, the algorithm is:  
Study Day = visit/examination date – date of first study drug administration + 1.

Summary data such as AEs will not be reported by visit.

Both scheduled and unscheduled visits and assessments will be used to determine minimum and maximum change from baseline. Tables that report abnormalities (e.g., laboratory shift tables) will include all assessments.

#### 4.3.3 Missing and partial data

The following rules for missing data will be followed:

- AE date imputations will follow the rules described in Appendix 1.
- The causality assessment for AEs should not be missing and will be queried for a value. AEs with missing causality will be considered related to study drug.

Unless otherwise specified, missing values for other individual data points will remain missing. Missing values will not be imputed and only observed values will be used in data analyses and presentation.

#### 4.3.4 Duration (e.g., for treatment exposure)

If date and time are collected, then duration is calculated as event end date and time minus event onset date and time. Duration will be displayed as days and fractions of days, or as hours and fractions of hours, as appropriate.

If only the date is collected, then the duration in days is calculated as event end date minus event onset date + 1.

#### 4.3.5 Elapsed actual time

For PK blood sampling, elapsed actual time in hours is the number of hours elapsed from date and time of study drug administration on related day. This time is derived from actual dates and times recorded in the electronic case report form (eCRF).

#### 4.3.6 Coding dictionaries

AEs, medical history, and procedures are to be coded using the Medical Dictionary for Regulatory Activities (MedDRA) Version 28.0 or later. Previous and concomitant treatments are to be coded using the World Health Organization Drug Dictionary Enhanced (WHO DDE) dated 01MAR2025 or later (format B3).

## **5 SUBJECT DISPOSITION**

### **5.1 Disposition**

The number and percentage of subjects screened, randomized, and included in each of the analysis sets will be summarized by cohort and treatment. The number and percentage of subjects who completed or discontinued from the study treatment and from study will also be presented, with the reason for discontinuation. All percentages will be based on the number of subjects in the safety set.

Subjects who failed screening and the reasons for screen failure will only be listed.

### **5.2 Protocol deviations**

A protocol deviation is any change, divergence, or departure from the study design or procedures defined in the protocol. Protocol deviations will be documented by the clinical monitor throughout the course of monitoring visits. The protocol deviations will be categorized as important and non-important deviations. The final list of protocol deviations will be approved prior to database lock and unblinding of the study.

All protocol deviations will be listed.

### **5.3 Inclusion and exclusion criteria**

Full inclusion and exclusion criteria are listed in the protocol Sections 5.1 and 5.2, respectively. Unmet inclusion and met exclusion criteria for each subject will be listed.

## **6 DEMOGRAPHICS AND BASELINE CHARACTERISTICS**

### **6.1 Demographics and general baseline characteristics**

The following demographics and baseline characteristics data will be presented in tables using descriptive statistics for the Safety and PK sets:

- Age, sex, childbearing potential, race, ethnicity
- Height, weight, and body mass index (BMI).

### **6.2 Medical history**

Medical history will only be listed.

## **7 TREATMENTS AND MEDICATIONS**

### **7.1 Prior and concomitant medications/ non-drug procedures**

Prior medications/ procedures are defined as medications/ procedures with a stop date prior to the first dose of study drug. Concomitant medications/ procedures are defined as medications/ procedures that are either ongoing at the start of the first dose of study drug or starting on or after the first dose of study drug.

Prior and concomitant medications and non-drug procedures will only be listed, separately, with each clearly identified as either prior or concomitant.

## 7.2 Study treatments

### 7.2.1 Study drug exposure

Descriptive statistics for the duration of study drug administration will be summarized for the Safety set.

Study drug duration is defined as:

*“Days of (Date of the last dose – Date of first dose) + 1”.*

### 7.2.2 Treatment administration

Treatment administration details will be listed.

## 8 PHARMACOKINETIC ANALYSIS

All PK analyses will be conducted using the PK set.

### 8.1 Plasma concentration

Plasma concentrations of fosmanogepix and manogepix will be analyzed at each time point of collection and will be summarized with descriptive statistics (n, mean, SD, coefficient of variation [CV%], minimum, median, maximum, and geometric mean).

#### *Treatment of outliers*

Individual concentration-time points, if considered anomalous, may be excluded from the analysis at the discretion of the pharmacokineticist and with approval from the Sponsor following a review of the available documentation. Any such exclusion will be outlined in the clinical study report.

Entire individual treatment profiles for a subject may be excluded following review of the available documentation. However, PK analyses may be performed with and without the excluded profiles. Any such exclusion will be clearly listed along with justification for exclusion.

#### *Non-quantifiable concentrations*

All concentration values reported as no results (not collected or not determined) values will be treated as missing. For the calculation of concentration summaries, all concentrations below the quantifiable limit (BLQ) will be treated as 0, except for geometric mean where BLQ values will be ignored. Values that are BLQ will be displayed as ‘BLQ’ in listings. If more than half of the concentrations are BLQ, only minimum, maximum and mean statistics will be calculated, with ‘BLQ’ for minimum and mean.

Plasma concentrations will also be summarized by cohort and treatment with the following figures:

- Plot of geometric mean versus scheduled sampling time, using linear and semi-log scale

- Plot of mean  $\pm$  SD versus scheduled sampling time, using linear and semi-log scale
- Plot of individual concentrations versus actual sampling time, using linear and semi-log scale
- Combined, by cohort and treatment, individual plasma concentrations versus actual sampling time, using linear scale and semi-log scale.

## 8.2 PK parameters

Individual PK parameters will be estimated using non-compartmental methods with WinNonlin®.

The plasma PK parameters will be estimated from the concentration-time profiles. In estimating the PK parameters, BLQ values at the beginning of the profile will be set to zero. BLQ values that occur after the first quantifiable point will be considered missing. Values that are embedded between BLQs, or quantifiable values occurring after two or more BLQs, will be set to missing at the discretion of the pharmacokineticist and in agreement with the Sponsor. Actual sampling times, rather than scheduled sampling times, will be used in all computations involving sampling times. If the actual time or dose time is missing, the scheduled time may be substituted in order to calculate the PK parameter.

The PK parameters to be determined or calculated using non-compartmental analysis from the plasma concentration-time data are:

**Table 1 Plasma PK parameters for Part-1: Single-dose**

Parameter	Analyte	Definition	Method of determination
AUC 0-24h	Manogepix/ fosmanogepix*	Area under the plasma concentration-time profile from time zero to 24 hours	Linear/log trapezoidal method.
AUC last	Manogepix/ fosmanogepix*	Area under the concentration-time curve from time zero to the time of the last quantifiable concentration (C last )	Linear/log trapezoidal method.
AUC inf *	Manogepix	Area under the concentration-time curve from time zero extrapolated to infinite time	AUC last + (C last */k el ), where C last * is the predicted plasma concentration at the last quantifiable time point from the log-linear regression analysis.
C max	Manogepix/ fosmanogepix*	Maximum plasma concentration	Observed directly from data.
T max	Manogepix/ fosmanogepix*	Time for C max	Observed directly from data as time of first occurrence.

Parameter	Analyte	Definition	Method of determination
$t_{1/2}^*$	Manogepix	Terminal elimination half-life	$\text{Log}_e(2)/k_{el}$ , where $k_{el}$ is the terminal phase rate constant calculated by a linear regression of the log-linear concentration-time curve. Only those data points judged to describe the terminal log-linear decline will be used in the regression.
$CL^*$ (Cohort 2 only)	Manogepix	Clearance	$\text{Dose}/AUC_{inf}$ .
$CL/F^*$ (Cohort 1 only)	Manogepix	Apparent clearance	$\text{Dose}/AUC_{inf}$ .
$V_{ss}^*$ (Cohort 2 only)	Manogepix	Volume of distribution at steady state	$CL \times MRT$ , where MRT is the mean residence time calculated for single IV dose as $AUMC_{inf}/AUC_{inf} - (DOF/2)$ , where $AUMC_{inf}$ is the area under the moment curve from time 0 extrapolated to infinity, and DOF is the duration for IV infusion dose.
$V_z/F^*$ (Cohort 1 only)	Manogepix	Apparent volume of distribution	$\text{Dose}/(AUC_{inf} \times k_{el})$ .
$F^*$	Manogepix	Absolute bioavailability	$AUC_{inf,po}(\text{dose normalized})$ (mean value in Cohort 1) / $AUC_{inf,iv}(\text{dose normalized})$ (mean value in Cohort 2)
$f_u$	Manogepix	Fraction of unbound drug in plasma	Obtained from measurement of protein binding (determined by assay lab)

\* As data permit.

**Table 2 Plasma PK parameters for Part-2: Multiple-dose**

Parameter	Analyte	Definition	Method of determination
$AUC_{tau}$	Manogepix/ fosmanogepix*	Area under the plasma concentration-time profile from time zero to the time of the end of the dosing interval (tau), where tau = 24 hours	Linear/log trapezoidal method.
$C_{max}$	Manogepix / fosmanogepix*	Maximum plasma concentration	Observed directly from data.
$T_{max}$	Manogepix / fosmanogepix*	Time for $C_{max}$	Observed directly from data as time of first occurrence.

Parameter	Analyte	Definition	Method of determination
$t_{1/2}^*$	Manogepix	Terminal elimination half-life	$\text{Log}_e(2)/k_{el}$ , where $k_{el}$ is the terminal phase rate constant calculated by a linear regression of the log-linear concentration-time curve. Only those data points judged to describe the terminal log-linear decline will be used in the regression.
$CL^*$ (Cohort 3 only)	Manogepix	Clearance	$\text{Dose}/AUC_{\tau}$ .
$CL/F^*$ (Cohort 4 only)	Manogepix	Apparent clearance	$\text{Dose}/AUC_{\tau}$ .
$V_{ss}^*$ (Cohort 3 only)	Manogepix	Volume of distribution at steady state	$CL \times MRT$ , where MRT is the mean residence time calculated as $[AUMC_{\tau} + \tau(AUC_{inf} - AUC_{\tau})] / AUC_{\tau} - (DOF/2)$ , where $AUMC_{\tau}$ is the area under the moment curve from time 0 until the end of the dosing interval ( $\tau$ ), and DOF is the duration of the IV infusion dose.
$V_z/F^*$ (Cohort 4 only)	Manogepix	Apparent volume of distribution	$\text{Dose}/(AUC_{\tau} \times k_{el})$ .
$C_{\text{trough}}$	Manogepix	Pre-dose concentration	Observed directly from data obtained on Day 7 and Day 8 (24 hours after last dose) # .
F	Manogepix	Absolute bioavailability	$AUC_{\tau,po}(\text{dose normalized}) (\text{mean } AUC_{\tau} \text{ in Cohort 4}) / AUC_{\tau,iv}(\text{dose normalized}) (\text{mean } AUC_{\tau} \text{ in Cohort 3})$

\* As data permit.

# Other pre-dose concentrations will be collected on Day 1 (second dose), Day 2, Day 3, and Day 6.

If multiple maxima occur at equal concentrations, the first temporal value will be taken for  $T_{\max}$ . The number of data points included in the regression of  $k_{el}$  and  $t_{1/2}$  after single dose will be determined by visual inspection, but a minimum of 3 data points in the terminal phase, excluding  $C_{\max}$ , will be required to estimate  $k_{el}$ . The  $k_{el}$  values (and consequently  $t_{1/2}$ ,  $CL/F$ ,  $V_z/F$ ,  $AUC_{inf}$ ) will be considered unreliable estimates – and therefore excluded from analysis – if the period of time over which an individual  $k_{el}$  was estimated is less than twice the resultant  $t_{1/2}$  or if the adjusted coefficient of determination R-squared is less than or equal to 0.75.

The proportion of  $AUC_{inf}$  due to extrapolation ( $AUC_{extrap}$ ) will also be calculated and expressed as a percentage. The value of  $AUC_{extrap}$  should be less than or equal to 20% for  $AUC_{inf}$  to be considered to be well estimated. If  $AUC_{extrap}$  is higher than 20%, then the values of  $AUC_{inf}$ ,  $CL/F$ ,  $V_z/F$ ,  $t_{1/2}$ , and  $k_{el}$  will be considered unreliable and therefore excluded from the summaries.

All PK parameters will be summarized with descriptive statistics (n, mean, SD, CV, minimum, median, maximum, geometric mean, and geometric CV). For  $T_{\max}$ , only n, median, minimum and maximum will be presented. All parameters will be listed, and those

that compromise the reliability of other parameters (e.g.,  $AUC_{extrap}$ ,  $k_{el}$ ) will be marked with an indication.

Box and whisker plots of PK parameters  $C_{max}$ ,  $AUC_{0-24h}$ ,  $AUC_{inf}$ , and  $AUC_{tau}$  will be provided, as applicable. For Part-2, trough concentrations over time will be plotted (mean and SD) for manogepix by study day.

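### The reliability exclusions in SAP 8.2 name parameters that do not match the formulas in Tables 1 and 2, and the regression-span rule drops values because the half-life is long, so summarised half-life can be biased low

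*SAP*

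**What the plan says.** After Table 2, SAP Section 8.2 sets three reliability triggers.

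- **Span:** the period over which kel "was estimated is less than twice the resultant" half-life.
- **Fit:** "or if the adjusted coefficient of determination R-squared is less than or equal to 0.75".
- **Extrapolation:** AUCextrap above 20%.

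For the first two, the kel "values (and consequently" t1/2, CL/F, Vz/F and AUCinf) "will be considered unreliable estimates – and therefore excluded from analysis – if the period of time over which an individual" fails the test. For the third, AUCinf, CL/F, Vz/F, t1/2 and kel "will be considered unreliable and therefore excluded from the summaries". Neither sentence mentions CL or Vss.

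The number of regression points after a single dose "will be determined by visual inspection, but a minimum of 3 data points in the terminal phase" is required. All parameters are listed, with a mark on those that compromise the reliability of others. The section does not commit to a second summary that includes the excluded values.

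**The concern.** There are two separate problems.

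First, the list of dependent parameters should follow from the formulas in Tables 1 and 2, and it does not. Read literally, oral and IV clearance are filtered on different rules. These are primary endpoints (SAP 3.2.1), with six subjects per active dose in Part-1 and eight per cohort in Part-2.

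Second, the span trigger compares a quantity limited by the sampling schedule with the subject's own estimated half-life. A long half-life therefore causes its own removal, so any resulting bias in summarised t1/2 is downward. Protocol 4.3.1 says that the data will support a PK comparison with non-Chinese populations, and a truncated half-life would carry into that comparison.

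**Working it through.** The plan states no figure for this point, so there is none to reproduce.

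**Step 1. The list against the formulas (SAP Tables 1 and 2).**

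| Part, cohort | Parameter | Formula | Needs kel or AUCinf? | Named for exclusion? |
|---|---|---|---|---|
| 1, Cohort 1 | CL/F | Dose/AUCinf | yes | yes |
| 1, Cohort 1 | Vz/F | Dose/(AUCinf × kel) | yes | yes |
| 1, Cohort 2 | CL | Dose/AUCinf | yes | **no** |
| 1, Cohort 2 | Vss | CL × (AUMCinf/AUCinf − DOF/2) | yes | **no** |
| 2, Cohort 4 | CL/F | Dose/AUCtau | no | **yes** |
| 2, Cohort 4 | Vz/F | Dose/(AUCtau × kel) | yes | yes |
| 2, Cohort 3 | CL | Dose/AUCtau | no | no |
| 2, Cohort 3 | Vss | CL × MRT, where MRT contains AUCinf − AUCtau | yes | **no** |

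Four of the eight rows disagree with the formulas. This step needs no assumption about half-life.

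**Step 2. Where the span rule cuts.** The last sample is at 240 h in Part-1 and 360 h after the last dose in Part-2 (Protocol 1.3, PK sampling schedules). The cut-off is t1/2 = (last sample − first regression point)/2.

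- Part-1, fit from 48, 72 or 96 h: (240 − 48)/2 = 96 h, (240 − 72)/2 = 84 h, (240 − 96)/2 = 72 h.
- Part-2, same starts: 156, 144 and 132 h. From 144 h (the last three points): (360 − 144)/2 = 108 h.

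For comparison, under mono-exponential decline the extrapolated share is 2^(−240/t1/2). It reaches 20% at t1/2 = 240 × ln 2/ln 5 ≈ 103 h. At 96, 84 and 72 h it is 17.7%, 13.8% and 9.9%. For these three starts the span rule acts before the extrapolation rule. The start is chosen visually, so the analyst's choice moves the cut-off.

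**Step 3. Possible size.** The readable text gives neither a manogepix half-life nor its variability, so both are assumed. The model was a one-compartment 3-hour infusion with Part-1 sampling times, 10% residual error, CV 30% on clearance and 15% on volume. It used 4,000 subjects per scenario, a 48–240 h fit and all three triggers. Ratios are geometric mean of retained values to truth.

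| Median t1/2 | Excluded | Chance of losing at least 1 of 6 | t1/2 ratio | AUCinf ratio |
|---|---|---|---|---|
| 30 h | 0% | 0.00 | 1.00 | 1.00 |
| 48 h | 2% | 0.11 | 0.99 | 0.99 |
| 60 h | 8% | 0.40 | 0.95 | 0.96 |
| 72 h | 18% | 0.71 | 0.90 | 0.92 |
| 96 h | 50% | 0.98 | 0.76 | 0.82 |

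- **Narrow window (96–240 h):** 12% are excluded at a median of 48 h. At 72 h, 49% are excluded and the t1/2 ratio is 0.77.
- **Half-life driven by volume** (CV 10% on clearance, 30% on volume), median 72 h, 48–240 h: the t1/2 ratio is still 0.90 but the AUCinf ratio is 0.99.
- **Sampling to 360 h,** median 72 h: 1.3% are excluded and the ratio is 0.99 when fitting from 48 h; 13% and 0.92 when fitting from 144 h.
- **All estimable values kept:** the t1/2 ratio is 1.00–1.03 and the AUCinf ratio 1.00–1.02.

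A closed-form check on a lognormal half-life with median 72 h, CV 35% and a fit from 72 h runs as follows. σ = √ln(1 + 0.35²) = 0.340 and z = ln(84/72)/0.340 = 0.453. The share dropped is 1 − Φ(z) ≈ 33%, and the geometric mean ratio is exp(−σφ(z)/Φ(z)) ≈ 0.83, or −17%.

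**Step 4. Effect of the list mismatch on Part-1 clearance.** If CL is summarised on everyone while CL/F is filtered, the CL summary is lower than on retained subjects by 1%, 4%, 8% and 19% at medians of 48, 60, 72 and 96 h (48–240 h window, clearance-driven), with no true difference between routes.

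**The case against.** The strongest defence of the list is that it is loose wording. In Part-1, CL and Vss are reported as data permit, and once AUCinf is out they lose their input, so a careful programmer would probably drop them. That is plausible, but the SAP does not say it. For Part-2 one can argue that CL/F is not a consequence of kel and so escapes the first sentence, or that the paragraph concerns single dosing only. But the extrapolation sentence names CL/F outright, and a single-dose-only reading would leave Part-2 t1/2, Vz/F and Vss with no reliability rule. Either reading needs a correction.

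On bias, several stronger readings are tempting and the documents do not support them.

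- **That t1/2 and AUCinf are biased low as a matter of fact.** The readable text gives no half-life. At a median of 48 h or less with a wide window the effect is negligible, and AUCinf is materially affected only if a long half-life reflects low clearance.
- **That subjects are removed.** Only parameter values are. Cmax, AUC0-24h, AUClast and AUCtau are not named, and excluded values stay in the listings. A listing does not correct a summary table, however.
- **That bioavailability is distorted by the route mismatch.** Part-1 F uses AUCinf, which is filtered for both routes, and Part-2 F uses AUCtau.
- **That slow eliminators are lost to the safety evaluation.** Safety uses the Safety set, and no exposure–safety analysis is planned.
- **That the fit trigger is also a half-life rule.** It is not. In the simulations it added at most 3% of exclusions with fits from 24 or 48 h, and 7% at the extreme.
- **That the SAP already offers a with-and-without analysis.** The sentence "However, PK analyses may be performed with and without the excluded profiles" concerns whole profiles removed as outliers, so it neither remedies this point nor needs editing for it.

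One might also want to keep AUCinf whenever extrapolation is within 20%, whatever the span. That is debatable, because AUCextrap is computed from the same kel.

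**Conclusion.** The mismatch between the exclusion list and Tables 1 and 2 is established from the SAP text alone and affects primary endpoints. It should be corrected before the analysis.

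The selection effect of the span rule is also real in direction, but its size is conditional. For Part-1 it is about 0–1% on t1/2 at a median of 48 h or less, about 5% at 60 h and about 10% at 72 h with a 48–240 h window. It is larger with a narrower window and smaller with Part-2's longer sampling. These figures rest on the assumed one-compartment model and variability. The right statement is that summarised t1/2 can be biased low, and AUCinf too if half-life varies through clearance.

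**What to change.** 1. **Part-1:** whenever AUCinf is excluded, also exclude Cohort 2 CL and Vss, as is done for Cohort 1 CL/F and Vz/F.
2. **Part-2:** a kel failure removes t1/2, Vz/F (Cohort 4) and Vss (Cohort 3). Neither the kel nor the extrapolation rule removes CL or CL/F. State that the reliability rules apply to both parts.
3. **Both parts:** report the number of excluded values per arm and reason. Summarise t1/2, AUCinf and the parameters derived from them with and without values that fail the span or extrapolation rule.

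Leave the 20% and span thresholds, the choice of main summary and the outlier paragraph in Section 8.1 as they are.

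The cost is a revised paragraph and one extra table, in which some less precise values appear, flagged. Making the change before the values are seen avoids the appearance of a data-driven choice.
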